10. LIST OF FINAL REPORT TABLES, LISTINGS AND FIGURES

The TFL TOC provides the list of tables/listings and figures needed for the study report. It also identifies the tables eligible for each analyses and their role (synopsis, in-text, post-text, SHS, CTRS,...).

11. ANNEX 1 STANDARD DATA DERIVATION RULE AND STATISTICAL METHODS

11.1. Statistical Method References

The exact two-sided 95% CIs for a proportion within a group will be the Clopper-Pearson exact CI [Clopper CJ, Pearson ES. The use of confidence or fiducial limits illustrated in the case of binomial. *Biometrika*. 1934;26:404-413].

The standardised asymptotic two-sided 95% CI for the group difference in proportions is based on the method described in the following paper: Robert G. Newcombe, interval estimation for the difference between independent proportions: comparison of eleven methods, *Statist Med*. 1998; 17, 873-890]. The standardised asymptotic method used is the method six.

Dewé W, Durand Ch, Marion S *et al*. A multi-criteria decision making approach to identify a vaccine formulation. *Journal of Biopharmaceutical Statistics*, 2015; epublication ahead of print: DOI: 10.1080/10543406.2015.1008517.

11.2. Standard data derivation

11.2.1. Date derivation

- SAS date derived from a character date: In case day is missing, 15 is used. In case day and month are missing, 30 June is used.
- Onset day for an event (ae, medication, vaccination, ...): The onset day is the number of days between the last study vaccination & the start date of the event. This is 0 for an event starting on the same day as a vaccination. See SAS date derived in case the start date of the event is incomplete.
- Duration: Duration of an event is expressed in days. It is the number of days between the start & the stop dates + 1. Therefore duration is 1 day for an event starting & ending on the same day.
- Association of an event to the primary epoch: An adverse event belongs to the primary epoch, if the onset date is before and excluding Visit 5 or the last contact date, whichever is coming first.

11.2.2. Dose number

- The study dose number is defined in reference to the number of study visits at which vaccination occurred.
- Relative dose: the relative dose for an event (AE, medication, vaccination) is the most recent study dose given before an event. In case the event takes place on the day a study dose is given, the related dose will be that of the study dose, even if the event actually took place before vaccination. For instance, if an adverse event begins on the day of the study vaccination but prior to administration of the vaccine, it will be assigned to this dose.

11.2.3. Demography

- Age: Age at the reference activity, computed as the number of units between the date of birth and the reference activity. Note that due to incomplete date, the derived age may be incorrect by 1 month when month is missing from the birthdate. This may lead to apparent inconsistency between the derived age and the eligibility criteria/the age category used for randomization.
- Conversion of weight to kg

The following conversion rule is used:

- $\text{Weight in Kilogram} = \text{weight in Pounds} / 2.2$
- $\text{Weight in Kilogram} = \text{weight in ounces} / 35.2$

The result is rounded to 2 decimals.

- Conversion of height to cm

The following conversion rule is used:

- $\text{Height in Centimetres} = \text{Height in Feet} * 30.48$
- $\text{Height in Centimetres} = \text{Height in Inch} * 2.54$

The result is rounded to the unit (ie no decimal).

- Conversion of temperature to °C

The following conversion rule is used:

- $\text{Temperature in } ^\circ\text{Celsius} = ((\text{Temperature in } ^\circ\text{Fahrenheit} - 32) * 5) / 9$

The result is rounded to 1 decimal.

11.2.4. Immunogenicity

- For a given subject and given immunogenicity measurement, missing or non-evaluable measurements will not be replaced. Therefore, an analysis will exclude subjects with missing or non-evaluable measurements.
- A seronegative subject is a subject whose antibody titre/concentration is below the cut-off value of the assay. A seropositive subject is a subject whose antibody titre/concentration is greater than or equal to the cut-off value of the assay.
- The Geometric Mean Concentrations/Titres (GMC/Ts) calculations are performed by taking the anti-log of the mean of the log titre transformations. Antibody titres below the cut-off of the assay will be given an arbitrary value of half the cut-off of the assay for the purpose of GMT calculation. The cut-off value is defined by the laboratory before the analysis and is described in the protocol.
- In order to compute fold increase of antibody titres/concentrations (ratio) between post-vaccination and pre-vaccination titres/concentrations and for GMC/GMT calculation, antibody titres/concentrations below the assay cut-off will be given an arbitrary value of half the cut-off.
- *The cut-off for the updated (qualified) version of the PCA assay will be set at the level of the assay LLOQ (9.60 µg/mL). For results below the cut-off (LLOQ), an arbitrary value of half of the cut-off will be considered for calculation of GMC and fold increase.*
- *Considering cut-offs or neutralising antibody against RSV-A and RSV-B are below the assays' LLOQ, the following rules will be applied:*

Assay	Raw result	Derivation for seropositivity status	Derivation for GMT calculation	Derivation for fold-increase between Post and Pre-vaccination titres
Neutra RSV-A	<8	NEG	4	LLOQ/2
	[8-LLOQ[POS	8	LLOQ/2
	≥LLOQ	POS	Exact value	Exact value
Neutra RSV-B	<6	NEG	3	LLOQ/2
	[6-LLOQ[POS	6	LLOQ/2
	≥LLOQ	POS	Exact value	Exact value

- *Vaccine response to the RSV neutralising antibodies (anti-RSV-A and anti-RSV-B) will be defined as:*
 - *At least a 4-fold increase from pre-vaccination if pre-vaccination neutralising antibody titre <7 log₂ (<128).*
 - *At least a 3-fold increase from pre-vaccination if pre-vaccination neutralising antibody titre in [7-8] log₂ ([128-256]).*
 - *At least a 2.5-fold increase from pre-vaccination if pre-vaccination neutralising antibody titre in >8-10 log₂ (>256-1024).*

- *At least 1-fold from pre-vaccination if pre-vaccination neutralising antibody titre >10 log₂ (>1024).*
- *All CI computed will be two-sided 95% CI.*

11.2.5. Safety

- For a given subject and the analysis of solicited symptoms within 7 days post-vaccination, missing or non-evaluable measurements will not be replaced. Therefore the analysis of the solicited symptoms based on the Total Vaccinated Cohort will include only vaccinated subjects for doses with documented safety data (i.e., symptom screen completed). More specifically the following rules will be used:
 - Subjects who documented the absence of a solicited symptom after one dose will be considered not having that symptom after that dose.
 - Subjects who documented the presence of a solicited symptom and fully or partially recorded daily measurement over the solicited period will be included in the summaries at that dose and classified according to their maximum observed daily recording over the solicited period.
 - Subjects who documented the presence of a solicited symptom after one dose without having recorded any daily measurement will be assigned to the lowest intensity category at that dose (i.e., 37.5°C for fever or grade 1 for other symptoms).
 - Doses without symptom sheets documented will be excluded.
- For analysis of unsolicited adverse events, such as serious adverse events or adverse events by primary MedDRA term, and for the analysis of concomitant medications, all vaccinated subjects will be considered. Subjects who did not report the event or the concomitant medication will be considered as subjects without the event or the concomitant medication respectively.
- The preferred route for recording temperature in this study will be oral. For the analysis, temperatures will be coded as follows:

Grade	Temperature for oral, axillary or tympanic route	Temperature for rectal route
0	< 37.5°C	< 38.0°C
1	≥ 37.5°C - ≤ 38.5°C	≥ 38.0°C - ≤ 39.0°C
2	> 38.5°C - ≤ 39.5°C	> 39.0°C - ≤ 40.0°C
3	> 39.5°C	> 40.0°C

Note that for all tables described in this section, the way the percentage of subjects will be derived will depend on the event analysed (see table below for details). As a result, the N value will differ from one table to another.

Event	N used for deriving % per subject for Vaccination phase
Concomitant vaccination	All subjects with study vaccine administered
Solicited general symptom	All subjects with at least one solicited general symptom documented as either present or absent (i.e., symptom screen completed)
Solicited local symptom	All subjects with at least one solicited local symptom documented as either present or absent (i.e., symptom screen completed)
Unsolicited symptom	All subjects with study vaccine administered
Concomitant medication	All subjects with study vaccine administered

The intensity scale of the following solicited AEs will be assessed as described:

Adverse Event	Intensity grade	Parameter
Pain at injection site	0	None
	1	Mild: Any pain neither interfering with nor preventing normal every day activities.
	2	Moderate: Painful when limb is moved and interferes with every day activities.
	3	Severe: Significant pain at rest. Prevents normal every day activities.
Redness at injection site		Record greatest surface diameter in mm
Swelling at injection site		Record greatest surface diameter in mm
Fever*		Record temperature in °C
Headache	0	Normal
	1	Mild: Headache that is easily tolerated
	2	Moderate: Headache that interferes with normal activity
	3	Severe: Headache that prevents normal activity
Fatigue	0	Normal
	1	Mild: Fatigue that is easily tolerated
	2	Moderate: Fatigue that interferes with normal activity
	3	Severe: Fatigue that prevents normal activity
Gastrointestinal symptoms (nausea, vomiting, diarrhoea and/or abdominal pain)	0	Normal
	1	Mild: Gastrointestinal symptoms that are easily tolerated
	2	Moderate: Gastrointestinal symptoms that interfere with normal activity
	3	Severe: Gastrointestinal symptoms that prevent normal activity

*Fever is defined as temperature $\geq 37.5^{\circ}\text{C}$ for oral, axillary or tympanic route, or $\geq 38.0^{\circ}\text{C}$ for rectal route. The preferred route for recording temperature in this study will be oral.

The maximum intensity of local injection site redness/swelling will be scored at GSK Biologicals according to the standard GSK Biologicals' scoring system for adults:

- 0: ≤ 20 mm
- 1: > 20 mm to ≤ 50 mm
- 2: > 50 mm to ≤ 100 mm
- 3: > 100 mm

The maximum intensity of fever will be scored at GSK Biologicals according to the standard GSK Biologicals' scoring system for adults (via the preferred route for recording temperature in this study which is oral):

- 0: $< 37.5^{\circ}\text{C}$
- 1: $\geq 37.5^{\circ}\text{C}$ to $\leq 38.5^{\circ}\text{C}$
- 2: $> 38.5^{\circ}\text{C}$ to $\leq 39.5^{\circ}\text{C}$
- 3: $> 39.5^{\circ}\text{C}$

The investigator assessed the maximum intensity that occurred over the duration of the event for all unsolicited AEs (including SAEs) recorded during the study. The assessment was based on the investigator's clinical judgement.

For clintrial.gov and EudraCT posting purposes, a summary of subjects with all combined solicited (regardless of their duration) and unsolicited adverse events will be provided. Solicited adverse events will be coded by MedDRA as per the following codes.

Solicited symptom	Lower level term name	Lower level term code	Corresponding Primary Term code
Pain	Pain	10033371	10033371
Redness	Erythema	10015150	10015150
Swelling	Swelling	10042674	10042674
Fatigue	Fatigue	10016256	10016256
Fever	Fever	10016558	10037660
Gastrointestinal symptoms	Gastrointestinal disorder	10017944	10017944
Headache	Headache	10019211	10019211

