13. ANNEX 3 CALCULATION OF INDIVIDUAL AND OVERALL DESIRABILITY INDEX

The section below provide the details on how to calculate individual desirability index and overall desirability index score based on Annex E in the Protocol.

Reactogenicity

A logistic regression model will be fitted on each reactogenicity endpoint (any Grade 2/3 general AE and any related SAE, Grade 2/3 fever) reported during the 7-day follow-up period after vaccination, including all RSV formulations.

- The vaccine group as the fixed effect
- The age groups (18-32 years and 33-45 years) as the categorical covariant if deemed necessary.

The estimation of indication rate will be tabulated by treatment group. The SAS codes can be used as reference:

[figure not shown]
```
proc logistic data=React;
  class Treatment AgeGroup / param=glm;
  model response (event='AE')= Treatment| AgeGroup;
  lsmeans Treatment / ILINK e diff oddsratio adjust=bon cl;
run;
```

For any Grade 2/3 general AEs and any related SAEs, the incidence rate estimate (IR) will be transformed in a [0,1] desirability index using the following function:

$$DR1 = \begin{cases} \frac{1}{1 + \exp(-50 * (0.25 - IR))}, & \text{if } IR \leq 0.25 \\ \frac{1}{1 + \exp(-25 * (0.25 - IR))}, & \text{if } IR \geq 0.25 \end{cases}$$

where IR is the incidence rate estimated by the model. This function will allocate a desirability value of 1, 0.5 and 0 to incidence rate equal to 0.1, 0.25 and 0.5 respectively (see Figure 2). But the calculation equally weights Grade 2/3 general AEs and any related SAEs.

Figure 2 Desirability function for the incidence rate of Grade 2/3 general AEs and related SAEs - for each investigational RSV vaccine formulation

[figure not shown]

For Grade 2/3 fever, the incidence rate estimate (IR) will be transformed in a [0,1] desirability index using the following function:

$$DR2 = \frac{1}{1 + \exp(-120 * (0.05 - IR))}$$

where IR is the incidence rate estimated by the model. As illustrated in Figure 3, the function will allocate desirability values of 1, 0.5 and 0 to incidence rate equal to 0, 0.05 and 0.1 respectively.

Figure 3 Desirability function for the incidence rate of Grade 2/3 fever - for each investigational RSV vaccine formulation

Finally, the reactogenicity index will be computed by taking the geometric mean of the 2 indexes:

$$DR = \sqrt{DR1 * DR2}$$

Immunogenicity

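### The shared denominator for solicited general symptoms keeps women with no fever entry in the fever percentages as non-cases, against the section's own missing-data rules

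*SAP*

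**What the plan says.** The text at issue is in the current version, Amendment 4.

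- **Denominator (section 11.2.5).** For a solicited general symptom, N is "All subjects with at least one solicited general symptom documented as either present or absent (i.e., symptom screen completed"). Fever, headache, fatigue and gastrointestinal symptoms share this row; none has its own N.
- **Scope of that table (section 11.2.5).** "Note that for all tables described in this section, the way the percentage of subjects will be derived will depend on the event analysed". It is written for the tables of the section.
- **Templates 20 and 21.** Their footnotes also define N at the level of the record: subjects with the dose documented in Template 20, and subjects who returned the diary card in Template 21.
- **Missing data (section 11.2.5).** For solicited symptoms, "missing or non-evaluable measurements will not be replaced". Four rules follow, of which three matter here:
  - On absence: "Subjects who documented the absence of a solicited symptom after one dose will be considered not having that symptom after that dose".
  - A symptom marked present with no reading on any day "will be assigned to the lowest intensity category at that dose (i.e., 37.5°C for fever or grade 1 for other symptoms").
  - Where no sheet came back, the rule is exclusion: "Doses without symptom sheets documented will be excluded".
- **Desirability index (Annex 3).** "A logistic regression model will be fitted on each reactogenicity endpoint", and the fitted Grade 2/3 fever rate goes into DR2. According to the annex, "the function will allocate desirability values of 1, 0.5 and 0 to incidence rate equal to 0, 0.05 and 0.1 respectively". Annex 3 does not say who is in the fever model or how a blank fever response is coded.

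**The concern.** The listed rules cover a documented absence, a presence with readings, a presence without readings, and a sheet that was not returned. They do not cover a returned sheet on which another general symptom is answered and fever is left blank. The shared N settles that case by default: she is counted below the line and can never be counted above it. Arithmetically her missing fever status becomes no fever, although the section says missing values are not replaced and reserves the status of not having a symptom for a documented absence. Section 11.2.4 shows the alternative: for immunogenicity, the rule against replacement is followed by an explicit exclusion of subjects with missing measurements. For solicited symptoms the exclusion stops at the sheet.

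The direct consequence is that fever percentages in Templates 20 and 21 are biased downwards. A second consequence is possible. Grade 2/3 fever is one of the four components of the index that ranks the formulations, and DR2 is steep around 5%. If the fever model used the same N, a small understatement of the rate would raise the index.

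**Working it through.** **Inputs from the SAP (Annex 3).** DR2 = 1/(1 + exp(−120 × (0.05 − IR))), DR = √(DR1 × DR2) and D = DR^0.4 × DI^0.6. DR2 therefore enters D with exponent 0.5 × 0.4 = 0.2. Groups have about 100 women each (section 2).

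**Assumptions, because the SAP gives neither figure.** The true Grade 2/3 fever rate is p, and a share m of the women in N has fever blank. Blanks are unrelated to fever. DR1 and DI are held fixed and the age term in the model is ignored.

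**Step 1: the plan's own anchors.** DR2 at rates 0, 0.05 and 0.1 is 0.9975, 0.5000 and 0.0025. This agrees with the stated 1, 0.5 and 0 after rounding.

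**Step 2: effect on a table percentage.** With blanks kept in N as non-cases, the expected rate is p × (1 − m). At p = 5% and m = 2%, 5% and 10% it is 4.9%, 4.75% and 4.5%. This step needs no link to Annex 3.

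**Step 3: effect on DR2 and D, only if the shared N carries into the fever model.** D is multiplied by (DR2 at p(1 − m) ÷ DR2 at p)^0.2.

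| p | DR2 at p | m | p(1 − m) | DR2 | D multiplied by |
|---|---|---|---|---|---|
| 3% | 0.917 | 2% | 2.94% | 0.922 | 1.001 |
| 3% | 0.917 | 5% | 2.85% | 0.930 | 1.003 |
| 3% | 0.917 | 10% | 2.70% | 0.940 | 1.005 |
| 5% | 0.500 | 2% | 4.90% | 0.530 | 1.012 |
| 5% | 0.500 | 5% | 4.75% | 0.574 | 1.028 |
| 5% | 0.500 | 10% | 4.50% | 0.646 | 1.052 |
| 7% | 0.083 | 2% | 6.86% | 0.097 | 1.031 |
| 7% | 0.083 | 5% | 6.65% | 0.121 | 1.078 |
| 7% | 0.083 | 10% | 6.30% | 0.174 | 1.159 |

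**Step 4: the same check from counts.** Take 5 cases among 100 women in N. Keeping blanks gives 5/100 = 5% and DR2 = 0.500. Excluding 5 blanks gives 5/95 = 5.26% and DR2 = 0.422; excluding 10 gives 5/90 = 5.56% and DR2 = 0.339. With 2 cases the values are 0.973 with blanks kept, 0.970 with 5 excluded and 0.966 with 10 excluded.

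**Step 5: equal blank shares, unequal fever rates.** Because DR2 is non-linear, a common 10% blank share does not act equally on all groups. Between a group at 7% and one at 3%, the fever contribution to the ratio of D values is (0.0832/0.9168)^0.2 = 0.62 without blanks and (0.1736/0.9405)^0.2 = 0.71 with them. The gap narrows but the order does not change.

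**The case against.** **The link to DR2 is not in the document.** The N table governs section tables, whereas DR2 takes a logistic regression estimate. Annex 3 neither imports the N table nor codes a blank as no fever, and the reference PROC LOGISTIC code would drop a missing response by default unless the derived variable had already been set to no. This stands. A reader might infer that the SAP counts such women as fever-free in the rate behind DR2; the documents leave that open, so the DR2 and D figures are conditional.

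**A missing temperature is not always a fever-free record.** Fever marked present without any reading is set to 37.5°C, which is Grade 1. That woman is a fever case, though not a Grade 2/3 case. This stands too, and the point is limited to fever documented neither present nor absent.

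**The pattern may not occur.** If a completed symptom screen requires every item, no fever entry can be blank; the diary card and eCRF are not shown. That bears on the size, not on the rule as written, which admits a subject on one documented symptom.

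**The bias is small beside sampling error.** At 5% with 100 women the standard error is √(0.05 × 0.95/100) = 2.2 points, against a bias of 0.1 to 0.5 points. This is fair, but bias and noise are different things and the bias costs little to remove.

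**Nothing suggests that blanks differ between groups.** The 7-day window is observer-blind and allocation is randomised. A reader might infer that one formulation will be favoured by unequal blanks; the SAP offers no ground for that. The index is also described in section 6.4 as a descriptive tool.

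One passage should not be used in support. The SAP draft dated 10-NOV-2016 treated subjects who missed reporting symptoms as having none; later versions dropped that text.

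**Conclusion.** The point holds for the tables. Section 11.2.5 fixes a shared denominator that keeps a woman with no fever entry in the fever N as a non-case, and this conflicts with its own rules on missing values and documented absence. The direction is certain wherever such records exist: the fever percentage is too low by the factor (1 − m), if blanks are unrelated to fever.

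For DR2 the supportable finding is a gap: Annex 3 does not say how a blank fever response enters the model. If the shared N applies there, the effect matters only near or above the 5% midpoint and is about 0.5% of D or less at rates up to 3%, even with 10% blank. These sizes rest on assumed values of p and m. This is a minor point, worth correcting because correction is cheap.

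**What to change.** - In section 11.2.5, make N symptom-specific. For fever, include only subjects with fever documented as present or absent, or with at least one temperature recorded. Adapt the N footnotes of Templates 20 and 21 accordingly.
- In Annex 3, state that the Grade 2/3 fever model uses the same population, so that a blank fever response is neither coded as no nor left to software defaults.
- Show the number of subjects with fever status missing, by group. If it is zero throughout, that count closes the question and no result changes.

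The cost is a symptom-level N in the existing macro and one sentence in Annex 3. The downside is that N may vary slightly between rows of one table.

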Template 28 Exploratory comparisons between groups in terms of percentage of subjects reported any Grade 2/3 AE and/or any fever >38.5°C and/or any vaccine-related SAE during the 7-day (Days 0-6) post-vaccination period (Exposed set)

								Difference in percentage (Group 1 minus Group 2)			
										95 % CI	
Group 1	N	n	%	Group 2	N	n	%	Difference	%	LL	UL
30 PreF				Control				30 PreF - Control			
60 PreF				Control				60 PreF - Control			
120 PreF				Control				120 PreF - Control			
60 PreF				30 PreF				60 PreF - 30 PreF			
120 PreF				30 PreF				120 PreF - 30 PreF			
120 PreF				60 PreF				120 PreF - 60 PreF			

<each group>:

30 PreF = 30 µg PreF

60 PreF = 60 µg PreF

120 PreF = 120 µg PreF

Control = Placebo

N = Number of subjects with the administered dose

n/% = number/percentage of subjects reporting a specified symptom

95% CI = Standardized asymptotic 95% confidence interval, LL = Lower Limit, UL = Upper Limit

Template 29 Solicited and unsolicited symptoms experienced by at least 5 % of subjects, classified by MedDRA Primary System Organ Class and Preferred Term within the 30-day (Days 0-29) post-vaccination period including number of events - SAE excluded (Exposed set)

		<each group> N =		
Primary System Organ Class (CODE)	Preferred Term (CODE)	n*	n	%
At least one symptom				
<each SOC>	<each PT term>			

<each group>:

30 PreF = 30 µg PreF

60 PreF = 60 µg PreF

120 PreF = 120 µg PreF

Control = Placebo

At least one symptom = at least one symptom experienced (regardless of the MedDRA Preferred Term)

N = number of subjects with the administered dose

n* = number of events reported

n/% = number/percentage of subjects reporting the symptom at least once

Template 30 Distribution of change from baseline in haematology and biochemistry with respect to normal laboratory ranges (Exposed set)

			<each group >							
Laboratory parameter	Timing	Baseline PRE(D0)	Unknown		Below		Within		Above	
			n	%	n	%	n	%	n	%
Alanine Aminotransferase (ALT)	PI(D7)	Unknown								
		Below								
		Within								
		Above								
	PI(D30)	...								
PI(D60)	...									
PI(D90)	...									
Aspartate Aminotransferase (AST)	PI(D7)	Unknown								
		Below								
		Within								
		Above								
	PI(D30)	...								
PI(D60)	...									
PI(D90)	...									
Creatinine								
Eosinophils								
Haemoglobin								
Lymphocytes								
Neutrophils								
Platelet count								
White Blood Cells (WBC)								

<each group>:

30 PreF = 30 µg PreF

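### For the registry-posting AE summary, injection-site pain, redness and swelling are coded to MedDRA terms that drop the injection site

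*SAP*

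**What the plan says.** In section 11.2.5 of SAP Amendment 4, the intensity scale lists three solicited local events, each defined by its site: "Pain at injection site", "Redness at injection site" and "Swelling at injection site".

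Later in the same section, the SAP announces a summary for registry posting that combines all solicited and unsolicited events, and states: "Solicited adverse events will be coded by MedDRA as per the following codes". The table gives, in order, the symptom, the lower level term, its code and the primary term code. The three local rows read "Pain Pain 10033371 10033371", "Redness Erythema 10015150 10015150" and "Swelling Swelling 10042674 10042674". The same rows stand in every version of the main SAP, so this is current text and not a leftover.

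Template 29 in section 14 carries the title "Solicited and unsolicited symptoms experienced by at least 5 % of subjects, classified by MedDRA Primary System Organ Class and Preferred Term" and covers Days 0-29 with SAEs excluded. Its columns are number of events, number of subjects and percentage.

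**The concern.** The site is what makes these three events local. The coding table removes it at the lower level term and does not restore it at the primary term. A registry reader does not have the SAP and would take rows headed Pain, Erythema and Swelling as unlocalised events, although they consist largely or wholly of injection-site reactions.

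There is a second effect. Section 6.3.1.1 codes unsolicited events by matching each verbatim report to its own preferred term, and it recognises unsolicited local AEs. An unsolicited pain elsewhere on the body that is coded to Pain falls in the same row as the solicited injection-site pain. Conversely, an injection-site reaction reported as unsolicited may receive a site-specific term and land in a different row from the same kind of reaction collected on the diary. In both cases the row label does not describe what was counted.

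At stake is the accuracy of a public safety table, not any inference in the trial.

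**Working it through.** The SAP states no figure to reproduce, so the check sets the relevant text side by side and then sizes the effect under stated assumptions.

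**1. Collected event against assigned term (section 11.2.5).**
- Pain at the injection site is coded to Pain, 10033371, with primary term 10033371.
- Redness at the injection site is coded to Erythema, 10015150, with primary term 10015150.
- Swelling at the injection site is coded to Swelling, 10042674, with primary term 10042674.

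Three of three local symptoms lose the site qualifier, and none regains it at the primary term.

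**2. Whether the table layout repairs it (Template 29).** There is one row per preferred term. No column or footnote marks local against general or solicited against unsolicited. Take a subject with only solicited injection-site pain, and another with only an unsolicited pain elsewhere on Day 20 coded to Pain. Each adds one to the same row, and the table cannot separate them.

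**3. Size, on assumed incidences.** Let p be the proportion of a group with injection-site pain and q the proportion with an unsolicited event coded to Pain. Assume p = 0.30-0.60, q = 0.005-0.02, and that the two are independent.
- Row percentage: 1 − (1 − p)(1 − q) = p + (1 − p)q.
- Amount added by unsolicited events alone: (1 − p)q. The smallest value is 0.40 × 0.005 = 0.002; the largest is 0.70 × 0.02 = 0.014. That is 0.2-1.4 percentage points, or about 0.2-1.4 subjects in a group of about 100 (SAP Table 1).
- Share of the row with injection-site pain: p / [1 − (1 − p)(1 − q)]. At p = 0.30, q = 0.02: 0.30 / 0.314 = 95.5%. At p = 0.60, q = 0.005: 0.60 / 0.602 = 99.7%.

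On these inputs the row is almost entirely injection-site pain. Pooling barely changes the number; what is wrong is the label. A reader sees about 30-61% Pain where the assumed unsolicited figure is 0.5-2%. No comparable inputs are offered for Erythema or Swelling; for them only the loss of the label is shown.

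**The case against.** The strongest reply is that the information is not lost to the trial. Templates 22 and 23 tabulate unsolicited symptoms alone by preferred term over Days 0-29, Templates 18 and 19 tabulate solicited local symptoms alone, and Template 16 separates general from local symptoms. Pooling the two sources is the declared purpose of the posting summary. Section 14 also says that the mock titles and footnotes are illustrative and will be adapted, so a footnote could be added without recoding. The size above is assumed, and it shows that pooling hardly changes the count.

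Most of this stands, and it rules out several stronger readings:
- A reader might infer that genuine non-local events are hidden. Across the analysis as a whole they are not, because Templates 22 and 23 show them. In a table restricted to terms reaching 5% of subjects, a rare non-local event would not have had its own row anyway.
- A reader might infer a conflict with a local/general split used throughout the SAP. Templates 22 to 25 make no such split.
- A reader might infer that the posted table would exaggerate a vaccine-placebo contrast because local reactions differ most between groups. The SAP gives no incidence by group.
- A reader might infer that injection-site redness becomes indistinguishable from a rash elsewhere. That requires the rash to be coded to Erythema, which nothing in the SAP says.
- A reader might infer that local reactions move to particular system organ classes. The SAP does not print the class of any term.

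The reply does not reach the coding rule itself. That rule is fixed, not illustrative, and followed exactly it produces rows whose label omits the injection site. No planned footnote says otherwise.

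**Conclusion.** The point holds as a labelling and coding defect in one output. All three solicited local symptoms are assigned to terms without the injection-site qualifier, and the pooled table mixes them with any unsolicited event that receives the same preferred term. The mislabelling does not depend on the assumed incidences: it arises as soon as one of these rows is posted. The amount of mixing does depend on them, and is small (0.2-1.4 percentage points for Pain under the ranges above).

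The effect stops at the posting summary. The separate solicited and unsolicited tables are unaffected. So is the desirability index, which is built on general AEs, related SAEs, fever and antibody levels. The conclusion rests on one reading: section 11.2.5 does not name the posting table, and Template 29 is taken to be it because it is the only mock table in section 14 that pools solicited and unsolicited events by preferred term. The correction is worth making because it is cheap and the table is public; it does not bear on the primary objective.

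**What to change.** In the section 11.2.5 coding table, re-map the pain, redness and swelling rows to MedDRA terms that keep the injection-site qualifier, taking the codes from the MedDRA version in use. Leave the four general symptoms as they are. Then re-run Template 29 and any posting output built on the same lookup.

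If recoding is not possible, add a footnote to the Pain, Erythema and Swelling rows stating that they include solicited injection-site reactions. This corrects the label but still leaves solicited local and unsolicited events in one count.

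The cost is three lookup rows and a re-run. The drawback is that term names will differ from any earlier postings that used the old mapping, which should be noted alongside the posted table.
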